CR=complete response; CT=computed tomography; d=day; ECG=electrocardiogram; ECOG=Eastern Cooperative Oncology Group; FDG=[18F]-fluorodeoxyglucose; MRI=magnetic resonance imaging; NaF=sodium fluoride; PET=positron emission tomography; MRI=magnetic resonance imaging; Q6=every six; Q9=every 9; WOCBP=women of childbearing potential

<sup>a Chemistry samples will be collected every cycle during Cycles 1-4 and every other cycle (Cycle 6, Cycle 8, etc.) if results are stable, per Investigator discretion.

b CT/MRI of chest/abdomen/pelvis Q6 weeks (± 7d) through Week 36 relative to Cycle 1 Day 1 and Q9 weeks (± 7d) thereafter relative to Cycle 1 Day 1 until documented disease progression or subsequent anticancer therapy. Brain scan (MRI preferred) during screening is not required and should be performed per Investigator discretion based on clinical signs and symptoms. Additional brain MRI should be conducted if there are new clinical signs and symptoms suggestive of brain metastases. Bone metastases identified at baseline via a bone scan or PET (such as FDG-PET, NaF-PET, or other locally available PET options) to be followed at scheduled visits using localized CT or MRI as clinically indicated. If bone metastases cannot be seen on CT or MRI scans, bone scans or PET should be repeated, using the same diagnostic procedure bone metastases were at baseline, when CR is identified in target disease or when progression in bone is suspected.

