For those patients who have not progressed clinically or radiologically at the time of study drug discontinuation, every effort should be made to continue radiological tumor assessments every 12 weeks ( $\pm 7$  days) during survival follow-up, utilizing the same imaging modality as used at Screening as outlined in the Schedule of Assessments (Table 6), until progressive disease, initiation of subsequent anti-cancer therapy, withdrawal of consent, or study completion, whichever occurs first. Results of these scans should be assessed by RECIST v1.1 and data entered in EDC in the corresponding tumor assessment forms.

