## 11.2. Efficacy Assessments

## 11.2.1. Anti-tumor Efficacy Assessment

All sites of measurable and non-measurable disease must be documented at Screening and re-assessed at each subsequent tumor evaluation. Tumor assessment will be performed at the timepoints relative to Cycle 1 Day 1, as specified in the Schedule of Assessments (Table 6), regardless of drug (cycle) delays, skips, or interruptions. Tumor assessments will continue until disease progression, withdrawal of consent, initiation of subsequent anti-cancer therapy, or study completion, whichever occurs first.

Baseline imaging must include CT or magnetic resonance imaging (MRI) of the chest, abdomen, and pelvis. CT scans with IV contrast are the preferred method unless contraindicated (i.e., patients with contrast allergy or impaired renal clearance) and oral contrast may be used per Investigator's discretion. MRIs of the chest, abdomen, and pelvis with a noncontrast CT scan of the chest may be used in patients for whom CT scans with contrast are contraindicated. Bone scan or positron emission tomography (PET) scan (such as [18F]-fluorodeoxyglucose [FDG]-PET, sodium fluoride [NaF]-PET, or other locally available PET options) must also be performed in all patients to evaluate for bone metastases at baseline. At the Investigator's discretion, other methods of assessment of measurable disease per RECIST v1.1 may be used. Any CT, MRI, or bone imaging (bone scan or PET scan) obtained as standard of care prior to Screening visit will not need to be repeated as long as those imaging tests were obtained within 30 days prior to the date of enrollment.

After baseline tumor assessments, evaluation of tumor response per RECIST v1.1 will be performed every 6 weeks for the first 36 weeks following Cycle 1 Day 1 ( $\pm$ 7 days) and every 9 weeks thereafter ( $\pm$ 7 days), with additional scans performed as clinically indicated.

Post-baseline tumor assessments should use the same imaging modality (CT or MRI) as at baseline. Patients with bone metastases identified on the baseline bone scan or PET scan should be followed at scheduled visits using localized CT or MRI as clinically indicated. If the patient has bone metastases on the baseline bone scan or PET scan but are not visualized on CT or MRI, the same bone imaging modality (bone scan or PET scan) should be repeated when a complete response is identified in target disease or when progression in bone is suspected (Table 6).

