Tumor response criteria will be based on RECIST v1.1 (Eisenhauer, 2009) as cited in Section 17.4. A partial or complete response should be confirmed by a repeat scan not less than 4 weeks from the date the response was first documented per RECIST v1.1.

G1T28-213

For those patients who have not progressed clinically or radiologically at the time of study drug discontinuation, every effort should be made to continue radiological tumor assessments, utilizing the same imaging modality as used at Screening.

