^b CT/MRI of chest/abdomen/pelvis Q6 weeks (± 7d) through Week 36 relative to Cycle 1 Day 1 and Q9 weeks (± 7d) thereafter relative to Cycle 1 Day 1 until documented disease progression or subsequent anticancer therapy. Brain scan (MRI preferred) during screening is not required and should be performed per Investigator discretion based on clinical signs and symptoms. Additional brain MRI should be conducted if there are new clinical signs and symptoms suggestive of brain metastases. Bone metastases identified at baseline via a bone scan or PET (such as FDG-PET, NaF-PET, or other locally available PET options) to be followed at scheduled visits using localized CT or MRI as clinically indicated. If bone metastases cannot be seen on CT or MRI scans, bone scans or PET should be repeated, using the same diagnostic procedure bone metastases were at baseline, when CR is identified in target disease or when progression in bone is suspected.

Г

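### Protocol 10.1 and the Schedule of Assessments give different scan intervals for patients who stop drug without progression; if their later progression counts as a PFS event, the 12-week interval records it about 2 weeks later on average

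*Protocol*

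**What the plan says.** Protocol 10.1 covers patients who stop drug with neither clinical nor radiological progression. For them, during survival follow-up, "every effort should be made to continue radiological tumor assessments every 12 weeks" (±7 days). It does not say whether the 12 weeks run from the last scan, from discontinuation or from Cycle 1 Day 1. The results are to be read by RECIST v1.1 and entered in the database.

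The Schedule of Assessments (Protocol Table 6, footnote b) sets scans every 6 weeks through Week 36, then "Q9 weeks (± 7d) thereafter relative to Cycle 1 Day 1 until documented disease progression or subsequent anticancer therapy". SAP Appendix 1 repeats this, with the same stopping rule: "until documented disease progression or subsequent anticancer therapy". Neither has a 12-week schedule.

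Protocol 11.2.1 gives the same 6- and 9-week intervals and ties them to Cycle 1 Day 1, "regardless of drug (cycle) delays, skips, or interruptions". On stopping, it says: "Tumor assessments will continue until disease progression, withdrawal of consent, initiation of subsequent anti-cancer therapy, or study completion, whichever occurs first". Ending study drug is not in that list. Its last paragraph, on patients off drug, says only that "every effort should be made to continue radiological tumor assessments, utilizing the same imaging modality as used at Screening" and names no interval.

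On analysis, SAP 8.1.1 uses all scans up to the cutoff, and its PFS table (SAP Table 6) dates an event at the first documented progression. Another row of that table censors patients who stop treatment for a reason other than progression, at their last adequate scan without progression. No precedence between the two rows is stated.

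**The concern.** Two sites could scan the same kind of patient at 6 weeks and at 12 weeks, each following a section of the protocol. PFS is the primary endpoint, and progression is dated at the scan that shows it, so the interval feeds into the event date. A sparser schedule records progression later on average, which lengthens PFS. With a single arm, no concurrent control shares that delay.

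**Working it through.** **The plan's own figure.** Protocol Table 12 gives 36 events and 80% power at a hazard ratio of 0.70, and 38 events and 54% at 0.80. Inputs: 45 patients, 10-month accrual (taken as uniform), 14-month follow-up, control median 5.6 months, exponential times, two-sided 0.2.

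- Event probability: p1 = 1 − [exp(−14λ) − exp(−24λ)]/(10λ), with λ = HR × ln 2/5.6.
- HR 0.70: λ = 0.0866, p1 = 0.801, and 45 × 0.801 = 36.1 events.
- HR 0.80: λ = 0.0990, p1 = 0.841, and 45 × 0.841 = 37.9 events.
- The one-sample log-rank power formula then gives 79.5% and 53.6%.

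The plan's figures reproduce. No scan interval enters them, so this point leaves the stated sample size, events and power unchanged.

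**Delay per patient, by hand.** If progression falls evenly within an interval, the mean lag to the next scan is half the interval: 12/2 = 6 weeks off drug under 10.1, against 6/2 = 3 weeks or 9/2 = 4.5 weeks under the Schedule of Assessments. The extra lag is 3 or 1.5 weeks.

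Single cases vary, because the two grids do not align. Counting the 12 weeks from the last scan:

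| Last on-drug scan | True progression | 6/9-week schedule | 12-week schedule | Difference |
|---|---|---|---|---|
| Week 18 | Week 22 | Week 24 | Week 30 | +6 weeks |
| Week 30 | Week 43 | Week 45 | Week 54 | +9 weeks |
| Week 30 | Week 38 | Week 45 | Week 42 | −3 weeks |

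**Simulation, counting off-drug progression as an event.** True PFS is exponential with median 5.6 months (hazard ln 2/5.6 = 0.124 per month), in samples of 30. Patients stop drug without progression at an assumed constant hazard h, so the affected share is h/(h + 0.124).

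| h per month (assumed) | Share affected | 12 weeks counted from | Mean extra delay | Dated earlier | Largest delay | Rise in average N=30 median |
|---|---|---|---|---|---|---|
| 0.03 | 19% | last scan | 1.9 weeks | 19% | 9 weeks | about 0.1 month |
| 0.03 | 19% | discontinuation | 2.3 weeks | 31% | about 12 weeks | about 0.1 month |
| 0.06 | 33% | last scan | 2.0 weeks | 18% | 9 weeks | about 0.2 month |
| 0.06 | 33% | discontinuation | 2.3 weeks | 30% | about 12 weeks | about 0.2 month |

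A separate run fixed the share. Mean documented PFS over all patients lengthened by 0.04 month at a 10% share, 0.08 to 0.09 at 20%, 0.12 to 0.14 at 30% and 0.21 to 0.24 at 50%.

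The large-sample median moves only in steps of the scan grid. With a true median of 5.6 months it stayed at 6.9 months throughout. With a true median of 8.0 it did not move at 10% to 20%, rose by 0 to 0.4 month at 30%, and rose by about 0.9 to 1.4 months at 50%.

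**Simulation, letting the SAP's discontinuation row censor.** Off-drug scans then set no PFS date. The median was identical under both schedules in every scenario run.

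**Scale.** For exponential times, the standard error of the median at N = 30 is about 5.6/(ln 2 × √30) = 1.5 months. A shift of 0.1 to 0.2 month is roughly a tenth of that.

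**The case against.** The strongest reply is that the 12 weeks are a deliberate follow-up-phase schedule. In the Schedule of Assessments the scan mark appears under the treatment columns (the table layout is broken in the text available). Section 10.1 is confined to survival follow-up, and its reference to Table 6 follows the words on imaging modality. Section 11.2.1 names delays, skips and interruptions, but not permanent discontinuation. That reading is plausible, but no text states it, and footnote b's stopping rule (progression or new therapy) contradicts it. The conflict stands.

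The second reply is that the SAP overrides the protocol on analysis methods, and its discontinuation row may censor exactly these patients. This part stands as a condition. SAP 8.1.1 and the progression row point the other way. Protocol 12.4.6.1 also does not list stopping drug among the points that end PFS data. But the SAP does not settle it.

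A reader might infer three stronger claims that the documents do not support:

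- **PFS is biased upward whatever the rule.** It is not if the discontinuation row applies, and the effect is confined to patients who stop without progression and start no new therapy.
- **Each affected date is late, by 6 weeks at most.** Later dating holds only on average, and single delays can reach 9 weeks, or about 12 if counted from discontinuation.
- **The comparison with 5.6 months is distorted by a known amount.** The control's scan schedule is not given, and SAP 8.2.2 plans Kaplan-Meier description with no test against that figure.

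**Conclusion.** The scan intervals conflict, and the passages need reconciling. If off-drug progression counts as an event, as SAP 8.1.1 implies, the 12-week interval documents it about 2 weeks later on average per affected patient. The average median in samples of 30 rises by about 0.1 to 0.2 month. That size rests on exponential PFS with a true median of 5.6 months, discontinuation independent of progression, and an assumed 19% to 33% stopping drug first. If the SAP's discontinuation row censors these patients, the effect is nil. Net bias against the historical control cannot be computed. The severity is minor: the shift is small beside the sampling error at 30 patients, but it touches the primary endpoint and is cheap to settle.

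**What to change.** 1. **Protocol.** Reconcile 10.1 with the Schedule of Assessments and 11.2.1 so that one assessment schedule, counted from Cycle 1 Day 1, applies to every patient without progression, on or off drug.
2. **SAP Table 6.** State whether progression seen on a scan after drug was stopped is an event, or whether the discontinuation row censors the patient first.
3. **Data already collected.** If such progression counts as an event, add one PFS sensitivity analysis. Where progression was found after a visit in the Schedule of Assessments was skipped, date it at that skipped visit. Say in advance which visit is used if several were skipped.

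The cost is a wording change in each document and one extra analysis run. Sites that used 12 weeks would do the scans that the Schedule of Assessments already lists. Enrollment is closed at 30, so the protocol change helps only patients still being scanned, and items 2 and 3 carry most of the value.

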# 10.2. Discontinuation/Withdrawal from the Study

A patient may withdraw from the study at any time at his/her own request or may be withdrawn at any time at the discretion of the Investigator for safety, behavioral, compliance,

G1T28-213

or administrative reasons. At the time of discontinuing from the study, if the patient has not already discontinued study intervention, an End of Treatment Visit should be completed with assessments performed as shown in the Schedule of Assessments (Table 6).

If the patient withdraws consent for disclosure of future information, the Sponsor may retain and continue to use any data collected before such a withdrawal of consent.

If a patient withdraws from the study, he/she may request destruction of any samples taken and not tested, and the Investigator or designee must document this in the site study records.

If a patient withdraws consent for further study procedures, the site should clarify if the patient (or legally authorized representative where allowed by local regulation) remains open to survival contact and associated data collection. Public records may be used to verify survival status if permitted by institutional or country guidelines.

# 10.3. Lost to Follow Up

A patient will be considered lost to follow-up if he or she repeatedly fails to return for scheduled visits and is unable to be contacted by the study site.

In general, a patient is considered lost to follow-up after there are at least 3 documented attempts to contact the patient. It is recommended that 1 attempt is via certified letter to the patient.

# 10.4. Study and Site Start and Closure

The overall study begins when the first patient signs the informed consent form. The overall study ends when the last patient completes the last study-related phone-call or visit, discontinues from the trial or is lost to follow-up (i.e., the patient is unable to be contacted by the Investigator).

A study site is considered eligible to start participation in the study once all regulatory approvals are in place, site agreement contract is fully executed, and any other required documents are in place as required by Sponsor.

The end of study is event driven. That is, unless otherwise decided by the Sponsor, the study will continue until approximately 70% of patients enrolled in the study have died, which is estimated to be approximately 30 months after the first patient is enrolled.

The Sponsor reserves the right to close a study site(s) or terminate the study at any time for any reason. Study sites will be closed upon study completion. A study site is considered closed when all required documents and study supplies have been collected, a study-site closure visit has been performed, and the site has closed all regulatory activities with the Institutional Review Board (IRB)/Independent Ethics Committee (IEC).

The Investigator may be requested to initiate study-site closure at any time, provided there is reasonable cause and sufficient notice is given in advance of the intended termination. Should this occur with patients receiving study drug, the patients will transition to receive standard of care treatment by their healthcare provider outside of this study.

G1T28-213

Reasons for the early closure of a study site by the Sponsor or Investigator may include but are not limited to:

- Failure of the Investigator to comply with the protocol, the requirements of the IRB/IEC or local health authorities, the Sponsor's procedures, or Good Clinical Practice (GCP) guidelines
- Inadequate recruitment of patients by the Investigator
- Discontinuation of further development of trilaciclib

If the study is prematurely terminated or suspended, the Sponsor shall promptly inform the Investigators, the IECs/IRBs, the regulatory authorities, and any contract research organization(s) used in the study of the reason for termination or suspension, as specified by the applicable regulatory requirements. The Investigator shall promptly inform the patient and should assure appropriate patient therapy and/or follow-up.

G1T28-213

#### 11. STUDY ASSESSMENTS

Study procedures and their timing are summarized in the Schedule of Assessments (Table 6). Adherence to the study design requirements, including those specified in the Schedule of Assessments, is essential and required for study conduct. Immediate safety concerns should be discussed with the study Medical Monitor upon occurrence or awareness to determine if the patient should continue or discontinue study intervention.

The Investigator or Designee will maintain a screening log to record details of all patients screened and to confirm eligibility or record reasons for screening failure, as applicable.

Procedures conducted as part of the patient's routine clinical management (e.g., hematology, chemistry) and obtained before signing of the informed consent form (ICF) may be utilized for screening or baseline purposes provided the procedures met the protocol-specified criteria and are performed within the permitted 30-day Screening period.

# 11.1. Screening Assessments

The following information for screening failures should be recorded into appropriate eCRFs: patient identification (ID), demographic data, inclusion/exclusion criteria, eligibility status, and SAEs (if any). Patients may only be rescreened one time at the discretion of the Investigator. For abnormal laboratory values, a second test to confirm the first is permitted.

# 11.1.1. ER-, Progesterone Receptor-, HER2-Negative Status

Eligibility will be based on local ER-negative, progesterone receptor-negative, HER2-negative status from the most recent tumor biopsy report obtained prior to Screening.

Estrogen receptor/progesterone receptor negative status should be histologically or cytologically confirmed by local pathology IHC assessment (defined as <1% nuclei staining) and HER2 non-overexpressing status should be confirmed by local assessment of IHC (0 or 1+), by *in situ* hybridization (ratio <2.0), or by average HER2 gene copy number of <4 signals/nucleus) per 2018 ASCO CAP criteria.

#### 11.1.2. Enrollment

Eligibility will be determined prior to enrollment and the start of study treatment. All eligible patients will receive a unique patient ID number. Once a patient ID is assigned to patient, it can never be reassigned to another patient.

Eligible patients will be instructed on all protocol requirements, including any restrictions on concomitant medication usage.

Enrollment will be performed via Interactive Web Response System following confirmation that the patient is eligible for the study.

#### 11.1.3. Demographics

Age, gender, race, and ethnicity will be collected during the Screening period.

G1T28-213

## 11.1.4. Medical History and Breast Cancer Disease History

Medical and surgical history, including past and current conditions, will be collected. Concomitant medications taken within 30 days prior to the first dose of study drug through the End of Treatment Visit will be recorded.

Documentation of TNBC history, including date of diagnosis as well as BRCA classification (if available), will be collected.

Prior radiation, surgery, and systemic chemotherapy for TNBC will also be recorded.

## 11.2. Efficacy Assessments

## 11.2.1. Anti-tumor Efficacy Assessment

All sites of measurable and non-measurable disease must be documented at Screening and re-assessed at each subsequent tumor evaluation. Tumor assessment will be performed at the timepoints relative to Cycle 1 Day 1, as specified in the Schedule of Assessments (Table 6), regardless of drug (cycle) delays, skips, or interruptions. Tumor assessments will continue until disease progression, withdrawal of consent, initiation of subsequent anti-cancer therapy, or study completion, whichever occurs first.

Baseline imaging must include CT or magnetic resonance imaging (MRI) of the chest, abdomen, and pelvis. CT scans with IV contrast are the preferred method unless contraindicated (i.e., patients with contrast allergy or impaired renal clearance) and oral contrast may be used per Investigator's discretion. MRIs of the chest, abdomen, and pelvis with a noncontrast CT scan of the chest may be used in patients for whom CT scans with contrast are contraindicated. Bone scan or positron emission tomography (PET) scan (such as [18F]-fluorodeoxyglucose [FDG]-PET, sodium fluoride [NaF]-PET, or other locally available PET options) must also be performed in all patients to evaluate for bone metastases at baseline. At the Investigator's discretion, other methods of assessment of measurable disease per RECIST v1.1 may be used. Any CT, MRI, or bone imaging (bone scan or PET scan) obtained as standard of care prior to Screening visit will not need to be repeated as long as those imaging tests were obtained within 30 days prior to the date of enrollment.

After baseline tumor assessments, evaluation of tumor response per RECIST v1.1 will be performed every 6 weeks for the first 36 weeks following Cycle 1 Day 1 ( $\pm$ 7 days) and every 9 weeks thereafter ( $\pm$ 7 days), with additional scans performed as clinically indicated.

Post-baseline tumor assessments should use the same imaging modality (CT or MRI) as at baseline. Patients with bone metastases identified on the baseline bone scan or PET scan should be followed at scheduled visits using localized CT or MRI as clinically indicated. If the patient has bone metastases on the baseline bone scan or PET scan but are not visualized on CT or MRI, the same bone imaging modality (bone scan or PET scan) should be repeated when a complete response is identified in target disease or when progression in bone is suspected (Table 6).

Tumor response criteria will be based on RECIST v1.1 (Eisenhauer, 2009) as cited in Section 17.4. A partial or complete response should be confirmed by a repeat scan not less than 4 weeks from the date the response was first documented per RECIST v1.1.

G1T28-213

For those patients who have not progressed clinically or radiologically at the time of study drug discontinuation, every effort should be made to continue radiological tumor assessments, utilizing the same imaging modality as used at Screening.

